10.2.2 Analysis methods

For all assessments, the baseline will be defined as the most recently available data before the administration of 1st dose treatment.

Descriptive statistics will be provided by treatment group/country and by all for all of the endpoints, including primary and secondary ones. Frequency table will be provided for categorical data, while mean, standard deviation, maximum, minimum, median, inter-quartile range (IQR), and 95% two-sided confidence interval will be calculated for continuous measurements.

AEs and SAEs will be reported by treatment group/country and physiological systems as appropriate. The incidence of treatment-related AEs and SAEs between treatments will be analyzed by Cochran-Mantel-Haenszel test (CMH) test.

Incidence of AEs and SAEs will be analyzed by CMH test. Changes in physical examinations will be displayed for each individual system. Net changes from pre-treatment laboratory test results and vital signs will be analyzed by descriptive statistics.

Healing time from DSW creation to 100% re-epithelialization will be estimated by using Kaplan-Meier methods and compared between groups by using log-rank test. The healing time is defined as from DSW creation to the first 100% re-epithelialization with confirmation for at least 10 days apart, observed by the investigator and the first additional evaluator.

If the first 100% re-epithelialization is observed at any visit by Day 28 with confirmation for at least 10 days apart, the healing time is noted as the duration from the Day of DSW creation to the day of the first 100% re-epithelialization. The fulfilling of the visits and/or follow-ups after the 100% re-epithelialization date will not be taken into account to determine the healing time. If the 100% re-epithelialization is not observed by Day 28 visit, the healing time will be censored on day of the last visit up to Day 28 visit. If the 100% re-epithelialization is observed by Day 28 visit but no confirmation is made, the healing time will be censored on day of the last visit up to Day 28 visit. The censoring rules will be applied immediately once patients leave the study regardless the participation and/or completion of the long-term (360 days) follow-ups.

If patient develops grade 2 or above SAEs and should exit the study prematurely before Day 14, he/she should be excluded from the primary efficacy analysis, because early censor will result in under estimation of the healing time while treatment group (TWB-103+TegadermTM) is prone to have higher risk of developing treatment related SAE.

In the cases of TWB-103/placebo discontinuation due to allergic reaction or infection, wound assessments performed after onset of allergic reaction or infection will be excluded from statistical analysis.

Healing rates (complete wound closure) of patients at Days 7, 10 and 14 after DSW creation will be analyzed by CMH test. Healing percentage of wounds (ratio of healing and original areas) at Days 7, 10 and 14 after DSW creation will be analyzed by Analysis of variance (ANOVA) model with treatment group and country as factor. Score on short-form McGill pain questionnaire will be analyzed by using Analysis of covariance (ANCOVA) model with treatment group and country as factor and baseline characteristics as covariate. Vancouver Scar Scale will be analyzed by Wilcoxon ranked sum test. The score in each category (pigmentation, vascularity, pliability and height) and the sum score of all category in Vancouver Scar Scale will be analyzed.

All treatment group comparisons will be conducted with significance level of 0.05, using 2-tailed tests.

Demographics and baseline characteristics will be summarized for each group/country by using descriptive statistics.

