3. STUDY POPULATION

3.1 The Number of Patients to Be Enrolled

The sample size is determined to be 15 versus 15 evaluable (per-protocol for Phase I+II) patients (1:1 ratio) for Treatment versus Control groups, 30 evaluable patients in total. To ensure the completion of 30 evaluable patients, around 36 patients will be recruited.

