3.2 Inclusion Criteria

A patient is eligible for the study if all of the following apply:

1. Female/male patients, aged 20-65 years old
2. Presenting a split-thickness skin graft donor site wound with a minimum size of 15 cm² but no more than 100 cm², with a minimum width of 3 cm and with an approximate thickness of 0.010~0.012 inches. The graft cannot be harvested from a site from which a skin graft was previously obtained.
3. If the primary wound is a result of a thermal or chemical burn, the total body surface area of the said wound must be less than 15%.

Note: The burn area is estimated based on the method used at the local site. The Rule of Nines Chart (1% body surface area equals one patient's palm size) or Lund and Browder Chart are acceptable.

4. Females of childbearing potential must have a documented negative serum pregnancy test done at the screening visit, which is within 2 weeks prior the DSW creation and the treatment
5. Both male and female patients must agree to use highly effective contraceptives from signing informed consent to 30 days after the last dose administration. Acceptable contraceptive forms include:

- a. Established use of oral, injected or implanted hormonal methods of contraception
- b. Placement of an intrauterine device (IUD) or intrauterine system (IUS)
- c. Barrier methods of contraception: Condom or occlusive cap (diaphragm or cervical/vault caps)

6. Willing to comply with the study protocol and has signed the Informed Consent Form

Note: The rationale for the inclusion criteria is described as below.

1. The lower limit of age, 20 years old is set as the age to participate in clinical trial by self-responsibility (the legal age of consent is 20 years old in Taiwan and Japan). Upper limit 65 years old is set because elderly patients tend to be poor in compliance and have poor skin quality.
2. Maximum size of DSW, 100 cm², is set by the standard of the investigational product, and a minimum size of 15 cm² is set considering that smaller DSW can heal easily and the existing standard treatment is sufficient. Minimum width of 3 cm is defined based on commonly medical appliance used for DSW creation. The thickness (0.010 - 0.012 inches) of the split skin grafting is defined based on clinical practice. And then, to minimize the complexity of safety and efficacy evaluation, the skin graft should be obtained from the area that has no previous use for skin graft.

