6.11 Wound assessment

The wound assessment will be measured at all scheduled visits except the Screening Visit.

From Visit 2 (Day 0) to Visit 8 (Day 42), the investigator will determine the end of treatment based on the healing progress. Wound healing will be assessed based on the wound observation by the investigator and an additional evaluator. An additional evaluator who is not aware of the treatment given will evaluate based on photos of the wound. The additional evaluator will receive photos of the wound from CRO and will return the assessment to CRO. A second additional evaluator, who is also blinded, will

be requested when the discrepancy occurs between investigator and the first additional evaluator in the determination of 100% re-epithelialization.

The photos of wound will be taken under the following guidelines.

- (a) Cameras and rulers with the same brand and model will be used throughout the study.
- (b) The study staff who are trained will be in charge of taking photos following the guidelines for each study center.
- (c) Two different photos will be taken for each wound at each visit: one for the calculation of wound healing and the other as the reference of the wound location relative to the body part.
- (d) The wound area shown in the photo specific for calculation purpose, along with the provided ruler, should have sufficient size and quality for evaluation.
- (e) Images will be processed by the software, Image J.
- (f) The investigator and evaluator(s) will select the boundary of said wound in the photo manually and by the wand tool in Image J.
- (g) Calculate the wound size by Image J based on the area selected.
- (h) The healing percentage of wounds will be calculated by the ratio of healing area and original area (Day 0).

Complete wound closure is defined as skin 100% re-epithelialization without drainage or dressing requirements. Wound closure should be re-confirmed on Day 28 when the complete wound closure occurs by Day 14, or on Day 42 in the case that complete wound closure occurs at some point between Day 14 and Day 28.

During the 360 days of follow-up (Visit 9~12), recording of 100% re-epithelialization and the area of target wound are not required. Instead, potential long-term adverse

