7.2 Administration Visit

(Visit 2: Day 0)

Before DSW creation

- Perform physical examinations
- Obtain vital signs
- Obtain blood samples for hemogram and biochemical tests (the hematologic and biochemical tests conducted within 7 days prior to Day 0 are acceptable)
- Obtain blood samples for PRA test (the PRA test conducted within 7 days prior to Day 0 is acceptable)

After DSW creation

- Wound assessment (including the thickness of DSW)
- Apply study medications (treatment group: TWB-103+ TegadermTM; control group: placebo+TegadermTM)
- Dispense TegadermTM to patients
- Record adverse events
- Record concomitant treatments

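### Day 0 wound area, measured on every patient before dosing, is a covariate in neither the healing-time comparison nor the healing-percentage ANOVA; pre-specify an area-adjusted supporting analysis and an ANCOVA

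*Combined protocol and SAP*

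**What the plan says.** - **Healing time (10.2.2).** The primary endpoint "will be estimated by using Kaplan-Meier methods and compared between groups by using log-rank test". No covariate, stratum or area-adjusted sensitivity analysis is named.
- **Healing percentage (10.2.2).** It "will be analyzed by Analysis of variance (ANOVA) model with treatment group and country as factor". The only model with baseline covariates is the pain-score ANCOVA, and those covariates are not named.
- **Size range (3.2).** Eligible wounds measure 15 to 100 cm². The rationale for the lower limit is that it "is set considering that smaller DSW can heal easily and the existing standard treatment is sufficient". The upper limit is put down to the product standard.
- **Measurement (7.2, 6.11).** After wound creation and ahead of the first application, the Day 0 list includes "Wound assessment (including the thickness of DSW". Area is read from photographs, and "The healing percentage of wounds will be calculated by the ratio of healing area and original area (Day 0". Day 0 area therefore meets the definition of baseline in 10.2.2 (last value before the first dose).
- **Randomisation (4.2, 7.1).** Permuted blocks stratified by site only, done before the wound is created.
- **Size and level (3.1, 10.2.2).** 15 versus 15 evaluable patients; "To ensure the completion of 30 evaluable patients, around 36 patients will be recruited". "All treatment group comparisons will be conducted with significance level of 0.05, using 2-tailed tests".

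**The concern.** The permitted wound sizes span a 6.7-fold range (100/15). If larger wounds take longer to close, two things follow in a trial this small. A chance difference in wound size between the arms moves the estimated treatment effect, and size-related variation adds noise. Measured area cannot be balanced at randomisation, so the analysis is the only place to deal with it, and the data are already collected. If the baseline table shows an imbalance, the plan has no pre-specified analysis to show whether it explains the result. One chosen after unblinding would carry less weight.

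**Working it through.** **The plan's own figure.** The 30 evaluable patients cannot be reproduced: the plan gives no effect size, power or event rate and says the number is not power-based. Recruiting 36 implies a loss of 1 − 30/36 = 16.7%; no rate is stated.

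**Chance imbalance.** The SD of the standardised difference in mean area is √(2/n) for n per arm.
- n = 15: √(2/15) = 0.365. P(|difference| > 0.5 SD) = 2[1 − Φ(0.5/0.365)] = 17%; for 0.3 SD it is 41%.
- If area is uniform on 15–100 cm² (assumption), SD = 85/√12 = 24.5 cm². The SD of the difference in means is 24.5 × 0.365 = 9.0 cm², so the means differ by more than 10 cm² in 26% of trials.
- Conclusions are drawn on the ITT population, which could reach 18 per arm. Then √(2/18) = 0.333, and the 17% becomes 2[1 − Φ(1.5)] = 13%.

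**Effect on the primary comparison.** Simulation of 20,000 trials per setting, 15 per arm. Assumptions not in the documents: uniform area, control median 12.5 days, Weibull shape 3, healing read on exactly Days 3, 7, 10, 14 and 28, no dropout. The adjusted test regresses the log-rank scores on treatment and area.

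| Hazard ratio per SD of area | Type I error, log-rank, all trials | Type I error when imbalance > 0.5 SD: log-rank / adjusted | Power at treatment HR 2.5: log-rank / adjusted | Power at HR 2: log-rank / adjusted |
|---|---|---|---|---|
| 1.0 | 5.1% | 5.4% / 5.7% | 55% / 54% | 34% / 33% |
| 0.85 | 5.1% | 5.9% / 5.7% | 54% / 54% | 33% / 33% |
| 0.7 | 5.1% | 7.1% / 4.5% | 50% / 52% | 32% / 33% |
| 0.5 | 5.1% | 12.3% / 5.2% | 40% / 48% | 25% / 30% |

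**How strong are these assumptions?** The size range is 85/24.5 = 3.46 SD. A hazard ratio of 0.7 per SD means a 0.7^(−3.46) = 3.4-fold hazard difference between the smallest and largest wounds. With shape 3, that is a 3.4^(1/3) = 1.5-fold difference in healing time. For 0.5 per SD the figures are 11-fold and 2.2-fold.

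**Visit windows.** The visits have windows of ±1 to ±3 days, and 10.2.2 counts actual days. In smaller checks with these windows (800 runs; strengths per doubling of area), power was 42% for the log-rank against 39% for the score-adjusted test at a hazard factor of 0.65, and 37% against 37% at 0.5. The power gains in the table therefore depend on fixed visit days.

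**Healing percentage.** With correlation r between outcome and area, the standard error changes by √[(1 − r²) × 27/26], because adding area to treatment and country takes the residual degrees of freedom from 27 to 26. At r = 0.5 this is √(0.75 × 1.038) = 0.88, the precision of 30/0.779 ≈ 38 patients. Power at a true difference of 0.8 SD, ANOVA to ANCOVA:
- r = 0: 56% to 54%
- r = 0.3: 56% to 58%
- r = 0.5: 56% to 67%

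No document gives r.

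**The case against.** The strongest reply is that this is an exploratory first-in-human study with an admittedly arbitrary sample size, that its standard primary test is valid, and that changing it buys little.

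- **The protocol does not call area prognostic.** A reader might infer that it does. Section 3.2 speaks only of wounds below 15 cm², and a gradient above that is a reasonable inference. The one explicit statement about healing time, in 1.1, ties 7 to 21 days to graft thickness. This stands.
- **Area is already in healing percentage as the denominator.** This stands too. Dividing by Day 0 area removes scale, so only a residual dependence is left to adjust for. With a control median near 12.5 days, many wounds will sit at 100% by Day 14, which weakens any linear relation there.
- **The log-rank holds its error rate.** True over all trials. The 7% and 12% are conditional on an imbalance and do not show an invalid test.
- **The larger gains need strong assumptions.** A 2.2-fold healing-time range from area alone is large beside the 3-fold range (7 to 21 days) that the protocol attributes to thickness. With visit windows the score-adjusted test gained nothing. This rules out replacing the primary test.
- **Area adjustment leaves out site, the randomisation stratum.** Correct, but the planned log-rank leaves it out as well; that is a separate question.

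What survives is the omission itself: a baseline measure with a plausible link to healing, already collected, and no pre-specified way to use it.

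**Conclusion.** The point holds as a gap in the supporting analysis of healing time and in the healing-percentage model. It is not a defect in the validity of the primary test. At 15 per arm, an imbalance above 0.5 SD of area is expected in about 17% of trials. The planned log-rank would then reject a true null about 7% to 12% of the time, for assumed hazard ratios of 0.7 to 0.5 per SD of area. For healing time, power changes by between nil and a gain of about 8 points if area is prognostic, and the upper end rests on fixed visit days. For healing percentage, the change runs from a loss of 2 points (r = 0) to a gain of 11 (r = 0.5). True prognostic strength is unknown.

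A reader might infer that an adjusted test should become primary; the calculations do not support that. Nor do they support avoiding a Cox model. Its low null rejection rate (about 2%) appeared when all visits fell on fixed days. With visit windows it was about 6% in runs of 800 to 1,200 trials.

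**What to change.** In 10.2.2:

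1. Keep the unadjusted log-rank as the primary test.
2. Pre-specify a supportive area-adjusted comparison of healing time and report the adjusted hazard ratio with its confidence interval. Either a Cox model on actual visit days with log Day 0 area, or an area-adjusted log-rank, would serve. State the choice and the tie handling in advance.
3. Replace the healing-percentage ANOVA by an ANCOVA with treatment, country and log Day 0 area.
4. Optionally, add graft thickness as a sensitivity covariate. It is recorded on Day 0 but restricted to about 0.010–0.012 inches.
5. List Day 0 area by arm among the baseline characteristics.

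The cost is a few lines of text and code, one degree of freedom, and about 1 to 3 points of power in the adjusted analyses if area is not prognostic. No new data, visits or patients are needed. The wording should be final before unblinding.

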Study Product, Dose, Route, Regimen	TWB-103, allogeneic human fibroblasts + gelatin-based hydrogel, applied 2 to 3 times till 100% re-epithelialization or up to 10 days (around once every 3 days); a matching placebo, freezing solution with gelatin-based hydrogel, is used as the control and applied to patients in the same duration and dosing frequency as TWB-103.
Duration of Treatment	During the planned treatment period (14 days), each patient will receive TWB-103+Tegaderm™ or placebo+Tegaderm™ for up to 10 days or to the day of 100% re-epithelialization, whichever comes first, followed by Tegaderm™ alone application from Day 10 to Day 14 if failing to achieve 100% re-epithelialization by Day 10.
Study Visits	
Patients will be scheduled to attend the following visits:
 
1. Screening (within 2 weeks prior to DSW creation)2. Day 0 (treatment begins)3. Day 3 (\pm 1 day)4. Day 7 (\pm 1 day)5. Day 10 (\pm 1 day)6. Day 14 (\pm 2 days, end of treatment)7. Day 28 (\pm 3 days, Follow-up)8. Day 42 (\pm 3 days, Follow-up)

9. 90 ± 14 days after Visit 7 or Visit 8 (Follow-up)

10. 180 ± 14 days after Visit 7 or Visit 8 (Follow-up)

11. 270 ± 14 days after Visit 7 or Visit 8 (Follow-up)

12. 360 ± 14 days after Visit 7 or Visit 8 (Follow-up)

Note: (1) For patients with complete wound closure by Day 14, the confirmation of wound closure will be assessed on Day 28.

(2) Day 42 follow-up is only scheduled when the wound closure is not completed by Day 14 but is observed on Day 28. The wound closure will be re-confirmed on Day 42.

(3) If no Visit 8, Visit 9~12 should be scheduled following Visit 7.

(4) In case patients achieve 100% re-epithelialization before or at Day 10, patients will finish up the assessments on the day with 100% re-epithelialization. This day of 100% re-epithelialization will be the end of treatment and the remaining scheduled treatment visits, if applicable, will be dismissed.

Patient Assignment Patients who meet all eligibility requirements for entry into the study will be randomized into one of the treatment group or control group in 1:1 ratio as shown below:

Treatment Group:

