Depending on the thickness of the split skin grafting, the DSW should spontaneously re-epithelialize completely in 7 to 21 days. Optimum local care for these DSWs should facilitate the wound healing process and be cost-effective, while it should prevent associated complications, such as pain, discomfort, infection, and scarring and consider the patients' physical and mental well-being during the treatment process. Particularly pain and discomfort are reported to occur with more frequency from DSWs than on the recipient site^{2,3}.

TWB-103 is supplied as a two-component therapeutics consisting of one vial of living allogeneic fibroblasts (TWB-102 cells) and one vial of gelatin-based hydrogel (TWB-103 hydrogel). While the mechanism of healing is multi-modal, TWB-103 does not function as a barrier dressing, but rather than a "stimulus" or "aid" to wound healing. TWB-102 cells do not persist as occurs in a graft. It is believed that, upon application to the wound, the production of cytokines and growth factors by the living cells are the key factors responsible for the ability of TWB-103 to enhance healing by secondary intention.

Nonclinical studies have shown that the fibroblasts present within TWB-103 produce many of the signaling molecules, such as basic fibroblast growth factors (bFGF), platelet-derived growth factor (PDGF), and other growth factors and cytokines that are known to be beneficial to the various phases of wound healing (i.e. hemostasis, inflammation, proliferation, and remodeling). Additionally, TWB-103 can also

provide wound site a number of matrix proteins that play key structural roles in skin and in healing.

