2.2 Endpoints

2.2.1. Primary endpoints

The primary endpoint for this study is:

Phase I

Safety:

Incidence of treatment-related AEs and SAEs (including infections and bleeding)

Phase I+II

Efficacy:

The healing time from DSW creation to the first 100% re-epithelialization with confirmation for at least 10 days apart, assessed by the investigator

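### Healing is dated to the visit where closure is first seen, across an unassessed stretch from Visit 6 to Visit 7, so Kaplan-Meier medians run late; the visit windows also allow re-confirmation sooner than the 10-day rule permits

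*Combined protocol and SAP*

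**What the plan says.** The primary efficacy endpoint (section 2.2.1) is time from wound creation to first full re-epithelialization, "with confirmation for at least 10 days apart, assessed by the investigator".

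Section 10.2.2 fixes the date and the method: "the healing time is noted as the duration from the Day of DSW creation to the day of the first 100% re-epithelialization", and "Healing time from DSW creation to 100% re-epithelialization will be estimated by using Kaplan-Meier methods and compared between groups by using log-rank test". It also sets the censoring rule: "If the 100% re-epithelialization is observed by Day 28 visit but no confirmation is made, the healing time will be censored". No interval-censored method is named.

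The visits that can date or confirm closure (sections 7.3 to 7.5) are Day 3 ±1, Day 7 ±1, Day 10 ±1, Day 14 ±2 (Visit 6), Day 28 ±3 (Visit 7) and, for some patients, Day 42 ±3 (Visit 8).

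On re-confirmation, section 6.11 says: "Wound closure should be re-confirmed on Day 28 when the complete wound closure occurs by Day 14". It sends closures between Day 14 and Day 28 to Day 42. The Protocol Summary (Study Visits, note 2) says: "Day 42 follow-up is only scheduled when the wound closure is not completed by Day 14 but is observed on Day 28". For Visits 9 to 12, section 6.11 says that "recording of 100% re-epithelialization and the area of target wound are not required".

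The only expectation about timing is in section 1.1: "the DSW should spontaneously re-epithelialize completely in 7 to 21 days".

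**The concern.** Two points arise from setting the visit calendar beside the endpoint definition.

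1. **Late dating.** The upper part of the expected healing range falls where nobody is scheduled to look at the wound. Unscheduled visits (section 4.3.4) include a wound assessment, but they are for patients who need medical attention, so they fill the gap only by chance. Closure can only be seen after it happens, so every dating error is towards late. If an arm's true median lies near Day 14, small chance differences decide whether its Kaplan-Meier median lands around Day 14-16 or around Day 25-28. The gap between two arms can then look large with little or no true effect.

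2. **Rule against windows.** The endpoint needs 10 days between first closure and confirmation, but no passage ties the visit windows to that minimum. A healed patient who attends every visit in window may fail the rule and be censored. The plan does not say whether such a re-confirmation counts, which leaves a choice about who is an event in a 30-patient primary analysis.

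**Working it through.** **Dating error, from the windows alone.** Visit 6 spans Days 12-16 and Visit 7 Days 25-31. No scheduled visit can date an event to Days 17-24. A closure on Days 15-21 first seen at Visit 7 is late by at least 25 − 21 = 4 days and at most 31 − 15 = 16 days. If healing were uniform over Days 7-21 with visits on nominal days, half of closures would fall after Day 14. Those would be dated 10.5 days late on average (6.1 days over all patients).

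**Effect on the medians.** The documents give no expected median or spread, so this part rests on assumptions: lognormal healing, 15 per arm (section 3.1), whole-day visits uniform in their windows, log-SD 0.35. There were 1,500 simulated trials per scenario.

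| True median (days) | Mean Kaplan-Meier median (days) | Lateness (days) |
|---|---|---|
| 10 | 12.1 | 2.1 |
| 12 | 15.5 | 3.5 |
| 13 | 18.0 | 5.0 |
| 14 | 20.7 | 6.7 |
| 15 | 23.4 | 8.4 |
| 16 | 25.4 | 9.4 |
| 18 | 27.1 | 9.1 |

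Differences in mean Kaplan-Meier medians follow by subtraction. Each pair of unequal arms has a true difference of 2.0 days.

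| True medians | Mean Kaplan-Meier difference (days) | Trials with a difference of 8 days or more, either direction: log-SD 0.35 (0.25) |
|---|---|---|
| 10 v 12 | 15.5 − 12.1 = 3.4 | 10% (3%) |
| 13 v 15 | 23.4 − 18.0 = 5.4 | 58% (69%) |
| 14 v 14 | 0 | 49% (50%) |
| 16 v 18 | 27.1 − 25.4 = 1.7 | 14% (5%) |

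**Interval-censored estimates** on the first 400 trials of each scenario (log-SD 0.35). Each event enters as the interval from the last visit not closed to the first visit closed. Entries are the mean difference in days, with the interquartile range.

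| True medians | Lognormal interval-censored fit | Turnbull midpoints |
|---|---|---|
| 10 v 12 | 2.1 (1.2 to 3.1) | 2.5 (1 to 4) |
| 13 v 15 | 2.0 (0.5 to 3.3) | 2.6 (0 to 5.5) |
| 14 v 14 | 0.0 (−1.4 to 1.4) | −0.1 (−2 to 2) |
| 16 v 18 | 1.9 (−0.1 to 3.7) | 2.0 (0 to 6) |

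At 16 v 18 the wider of the two Turnbull median intervals averages 7.1 days.

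**The test.** Log-rank rejection under no effect (3,000 trials each) was 4.9% (both medians 14, log-SD 0.35), 5.5% (14, log-SD 0.25), 6.1% (12) and 5.0% (17). In a separate run at log-SD 0.3, exact times gave 6.2% and 6.0% (medians 14 and 18) and visit-dated times 5.7% and 6.5%, so visit dating does not inflate the error rate. Coarse dating over the whole schedule does cost power: rejection fell from 0.53 to 0.37 (14 v 11 days), 0.41 to 0.24 (16 v 13) and 0.27 to 0.13 (20 v 17).

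**Confirmation interval**, listing every allowed pair of whole days:

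- Visit 6 (12-16) to Visit 7 (25-31): 5 × 7 = 35 pairs, separation 9 to 19 days. One is under 10: Day 16 to 25 (9 days).
- Visit 7 (25-31) to Visit 8 (39-45): 7 × 7 = 49 pairs, separation 8 to 20 days. Three are under 10: 30 to 39 and 31 to 40 (9 days), 31 to 39 (8 days).
- Visit 5 (9-11) to Visit 7: minimum 14 days, no conflict.

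If 12 patients first close at Visit 6 and 8 at Visit 7, the expected number failing the rule is 12 × 1/35 + 8 × 3/49 = 0.34 + 0.49 = 0.83. The chance of at least one is 1 − (34/35)^12 × (46/49)^8 = 57%. Across the simulated scenarios (2,000 trials each) the mean loss was 0.8 to 1.7 events of 30.

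**Which visit confirms a first closure on Day 16.** The Protocol Summary note and section 7.5.2 allow a Day 42 visit only when closure is first found on Day 28, so this patient has none. Sections 4 and 6.11 speak of closure between Day 14 and Day 28, which could be read to give one. These passages need reconciling.

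**The case against.** The planned inference is the log-rank test, both arms share the schedule, and the test holds; no between-arm bias has been shown. All of that stands, and the test should stay.

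The plan never says that a difference in medians will be the effect size, and a large spurious gap would usually sit beside a non-significant test. At 14 v 14, with 4.9% rejections and 49% large gaps, at most 4.9/49 = 10% of the gaps could come with p < 0.05. This limits the harm. But the Kaplan-Meier estimate is the only one named specifically for healing time, and the general descriptive statistics in 10.2.2 would use the same late dates. The healing rates and percentages at Days 7, 10 and 14 avoid the gap, but they are secondary.

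The largest figures need medians close to Day 14, and the documents do not say where the medians lie. This also stands. Below about Day 14 the lateness is a few days and comes from the shorter visit gaps; the long gap drives a median only when fewer than half the wounds are closed at Visit 6. Day 14 is, however, the midpoint of the 7-21 day range in section 1.1.

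The confirmation conflict is confined to window extremes, and nominal visits are 14 days apart. The Day 16 case takes closure by Day 14 to mean Visit 6. The Day 30 and 31 cases take closure by Day 28 to mean Visit 7, which is how the censoring sentences in 10.2.2 put it. It is an edge case, and the lost-event count falls if visits cluster on nominal days.

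The parametric estimate above was tested on its own lognormal model. Data from three other shapes gave 1.6 to 2.3 days against a true 2.0 (13 v 15 and 10 v 12), so the result is not fragile there.

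**Conclusion.** Both points hold. The direction of the first is certain: visit dating can only delay the healing time. Its size depends on a healing distribution that the documents do not give. Under the lognormal assumptions the mean Kaplan-Meier median is about 2 days late for a true median of 10 and about 9 days late for 16-18. The difference between arms is badly distorted only when the medians lie near Day 14. The log-rank test remains valid.

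The second point is exact as arithmetic: visits within the stated windows can be 8 or 9 days apart against a 10-day minimum, and the literal consequence is to censor a healed patient who attended on time. The expected loss is small, 0.8 to 1.7 of 30 events with visits uniform in their windows. It still needs settling before unblinding, since the analysis is so small. This is a change that should be made; it does not threaten the validity of the trial.

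**What to change.** 1. **Sections 6.11 and 10.2.2, confirmation.** Require the Day 28 or Day 42 re-confirmation visit to be booked at least 10 days after the visit of first closure, within the existing window. First closure on Day 16 puts Visit 7 on Days 26-31; Day 30 puts Visit 8 on Days 40-45; Day 31 puts Visit 8 on Days 41-45. Alternatively, state that a re-confirmation visit inside its window counts as confirmation. In either case, reconcile the Protocol Summary note and section 7.5.2 with sections 4 and 6.11 on which visit confirms a first closure on Day 15 or 16.

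2. **Section 10.2.2, estimation.** Keep the log-rank test. Pre-specify an interval-censored analysis running from the last visit not closed to the first visit closed: a Turnbull estimate, with the median given as an interval where it falls in the gap; a parametric interval-censored estimate of the difference; and an interval-censored log-rank test as a sensitivity analysis. Do not report the difference in Kaplan-Meier medians alone as the effect size.

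The cost is SAP wording and one line on visit booking; no visit is added and no window changes. The downsides are a little more analysis, wider intervals and a parametric assumption for the difference. The information lost between Visits 6 and 7 is not recovered.
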